Appendix H

Validation Algorithm

Appendix I

GP CPRD Validation Questionnaire for the UK.TASH-D Study

Dear Colleague,

Thank you for completing this questionnaire as a practice connected to the CPRD database. The UK.TASH-D study will use the CPRD to investigate the treatment of first time traumatic anterior shoulder dislocation. As you know, shoulder dislocations often recur and we are investigating whether surgery makes recurrence less likely after a first episode. We will be completely reliant in the main phase of this study on electronic codes to identify recurrences.

Before starting the main phase, we need to know whether we can reliably identify ‘New dislocation episodes’ or whether these tend to be recorded as a ‘Review’ of the same problem (without a further dislocation occurring). Conversely, we need to know if codes apparently indicating a ‘further’ dislocation episode are in fact a ‘Review’ of the problem. We also need to confirm that codes recorded in primary care as ‘dislocation’ actually reflect this diagnosis, rather than less specific conditions affecting the shoulder.

We are therefore looking at a national sample of records that indicate a shoulder dislocation, and by completing the following questionnaire on your patient, you will help tell us:

- 1) Was this actually a traumatic shoulder dislocation?
- 2) Did further episodes occur over the following two years, and if so, how many true recurrences were recorded as ‘New’ episodes?
- 3) Were there any examples of ‘New’ recurrences being recorded as a ‘Review’ of the original problem?

If the coding proves valid and reliable, then a CPRD dataset will be linked to a Hospital Episode Statistics (HES) dataset to compare surgical versus conservative treatment (including physiotherapy) on recurrent dislocation rates. Our aim is that this will result in national pathway guidelines for the management of this condition in primary care.

Thank you in anticipation of your help

The UK.TASH-D study team.

Number	Question	Response (please tick)	
		Yes	No
1.	Is shoulder dislocation, an unstable shoulder, or shoulder instability caused by INJURY documented in the patient’s notes?	(If YES go to Q5)	(If NO go to Q2)
2.	Is shoulder trauma or shoulder injury documented in the patient’s notes?	(If YES go to Q3)	(If NO go to Q3)
3.	Do MRI or X-ray imaging reports confirm a diagnosis of traumatic dislocation by mentioning the presence of Hill Sachs, Bankart lesion, labral tear, labral detachment, dislocation, relocation, bony Bankart?	(If YES go to Q5)	(If NO go to Q4)

This project was funded by the National Institute for Health Research Health Technology Assessment (project number 14/160/01).

The views and opinions expressed therein are those of the authors and do not necessarily reflect those of the HTA, NIHR, NHS or the Department of Health.

4.	Do Hospital letters from specialists or physiotherapists confirm traumatic instability or traumatic shoulder dislocation?	(If YES go to Q5)	(If NO go to Q8)
5.	Is there any record of a dislocation prior to the CPRD first registration date at your practice?	(If YES go to Q6)	(If NO go to Q6)
6.	Are there any further dislocation codes in the record during the 2 years after the first dislocation code?	(If YES go to Q6b)	(If NO go to Q6c)
6b.	If YES is it clear (for each one) that this is a further dislocation episode rather than simply a review of the problem?	(If YES go to Q7)	(If NO go to Q7)
6c.	If NO, have there been any further dislocations recorded during the following 2 years that are not electronically coded?	(If YES go to Q7)	(If NO go to Q7)
7.	Are there any physiotherapy treatment codes for 2 years after the first dislocation code?	(If YES go to Q7b)	(If NO go to Q7c)
7b.	If YES is it clear that this physio code indicates the patient received physiotherapy for their shoulder?	(If YES go to Q8)	(If NO go to Q8)
7c.	If NO, is there any documentation that the patient has received physiotherapy for their shoulder without a code being entered?	(If YES go to Q8)	(If NO go to Q8)
8.	If your specific responses to this questionnaire indicate that this patient has not had a traumatic shoulder dislocation but your reading of the notes or your knowledge of the patient suggest they might have please tick the YES box, otherwise tick the NO box.	The end – thank you	The end – thank you

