CPRD Internal Validation. 100 random sets of notes of patients aged 16-35 years with first time T ASD will be identified in CPRD. First time T ASD will be those patients with at least two years of data (washout period) before a first time entry read code for shoulder dislocation and with at least a further two years of follow up coding. These notes will be assessed for: use of shoulder dislocation codes for traumatic dislocation; confirming first time shoulder dislocation; confirming traumatic cause; and assessing the subsequent codes used for further events. Physiotherapy referral codes regards physiotherapy will also be assessed especially in terms of data on frequency of therapy, place of therapy (hospital or community) or type of therapy. Overall, data quality and completeness will be assessed using the GP questionnaire service (Appendix I) provided by CPRD. This questionnaire is based on the validation algorithm in Appendix H. Those risk factors that may play an important role as predictors of further re-dislocation and that are identifiable in CPRD will also be recorded. This analysis would ascertain which factors are reliably identifiable in CPRD and inform any formal analysis in WP2 regards future predictors.

Prevalence Rates (External Validation). We will compare age-gender prevalence rates of first time dislocators identified in our study with those of similar studies in other settings [7, 20]. This will externally validate GP and primary care coding of this condition. This external validation study will itself provide first time age and gender prevalence data on traumatic anterior shoulder instability in the UK.

During work package 1, if the analysis of the notes indicates that first time dislocation coding and recurrent dislocation coding is poor then the study cannot proceed and will be STOPPED (Red Light). To quantify this if during our review of coding and free text entries on patients with first time T ASD, if the positive predictive value of CPRD codes is $\geq 75\%$ (% recorded according to READ/OXMIS codes that are confirmed in the free text search) then we will continue to Stage 2 (Green Light). We would also take this opportunity to estimate the sensitivity of T ASD coding by using the algorithm on CPRD codes of alternative coding diagnose to include, but not limited to, shoulder pain, rotator cuff disorder, shoulder OA.

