APPENDIX D

TABLE OF CPRD DISLOCATION READ CODES

Description	READ Code	Number of clinical events currently recorded in CPRD
Dislocation or subluxation of shoulder	S41.00	51,162
Dislocation of shoulder NOS	S41z.00	11,578
H/O: dislocated shoulder	14G5.00	6,724
Closed reduction of dislocation of shoulder	7K6G300	2,878
Closed traumatic dislocation of shoulder	S410.00	2,240
Recurrent dislocation of shoulder – anterior	N083A00	2,140
Anterior dislocation of shoulder	S410111	1,864
Recurrent joint dislocation, of shoulder region	N083100	1,321
Recurrent subluxation of shoulder – anterior	N083C00	599
Closed traumatic dislocation shoulder jnt. Anterior (sub-coracoid)	S410100	439
Closed traumatic dislocation shoulder joint, unspecified	S410000	439
Closed traumatic subluxation, shoulder	S412.00	288

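### The GP questionnaire pools dislocation with instability and never asks direction, so the 75% stop-go PPV would be judged on a broader condition than first-time traumatic anterior dislocation

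*Protocol*

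**What the plan says.** Section F (CPRD Internal Validation) sets the only numerical stop-go rule. The study moves to Work Package 2 if the PPV of the CPRD codes for first-time traumatic anterior shoulder dislocation is at least 75%. The numerator is defined as coded cases "that are confirmed in the free text search".

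The same section now has data quality assessed by the GP questionnaire, and the Protocol Amendment section says the questionnaire takes the place of obtaining 100 sets of notes. Its covering letter (Appendix I) says the team must confirm that dislocation codes reflect that diagnosis "rather than less specific conditions affecting the shoulder".

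The items that classify a case are these:

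- **Question 1** asks whether the notes document "shoulder dislocation, an unstable shoulder, or shoulder instability caused by INJURY documented". YES goes to question 5, past questions 3 (imaging) and 4 (hospital letters).
- **Question 4**, reached only after NO at questions 1 and 3, asks whether letters "confirm traumatic instability or traumatic shoulder dislocation".
- **Question 5** asks "Is there any record of a dislocation prior to the CPRD first registration date at your practice". YES and NO both lead to question 6.
- **Question 8** is a free judgement for patients whose earlier answers point away from traumatic dislocation.

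None of the questions asks whether the dislocation was anterior. That word appears only in the covering letter.

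**The concern.** The stop-go rule refers to a narrow condition: first-time, traumatic, anterior, and a dislocation. The questionnaire's confirming answers refer to a wider one, in which traumatic instability without dislocation and dislocation in any direction also earn a YES. The covering letter names the distinction that matters, and questions 1 and 4 remove it.

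This cannot be left to the analysis. A single tick covering three descriptions does not show which one was met, and a direction that was never asked cannot be recovered.

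At stake is the decision to run the main study. A code list with a PPV below 75% for the cohort's defining diagnosis could clear the threshold on the wider definition, and Work Package 2 would then rest on a diagnosis that had not been validated at the level the protocol requires.

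**Working it through.** The 75% is a chosen cut-off with no derivation in the protocol, so there is no figure to reproduce. The check is how a measured share on the wider definition translates to the narrow one.

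**Inputs**
- Threshold: 75% (Section F).
- Share of traumatic glenohumeral dislocations that are anterior: 95% (Section D). Applying it to the confirmed cases is an assumption.
- *u*, the share of confirmed cases with instability but no dislocation: not in the protocol. 5%, 10% and 20% are assumptions used to show a range.
- Validation sample: 100 (Section F). Return rate: 80% (Protocol Amendment). If 100 questionnaires are sent (assumption), 100 × 0.80 = 80 come back.

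**Step 1, sign.** Every case meeting the narrow definition in a set of notes also meets the wider one. For the same notes, the confirmed share is therefore equal to or higher than the narrow share.

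**Step 2, direction only.** Narrow PPV = measured PPV × 0.95.
- Measured 75%: 0.75 × 0.95 = 0.7125, about 71%.
- Measured value needed for 75%: 0.75 / 0.95 = 0.789, about 79%.

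**Step 3, direction and instability.** Narrow PPV = measured PPV × (1 − *u*) × 0.95.

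| *u* (assumed) | Narrow PPV at a measured 75% | Measured PPV needed for a narrow 75% |
|---|---|---|
| 5% | 0.75 × 0.95 × 0.95 = 67.7% | 83.1% |
| 10% | 0.75 × 0.90 × 0.95 = 64.1% | 87.7% |
| 20% | 0.75 × 0.80 × 0.95 = 57.0% | 98.7% |

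**Step 4, effect on the decision.** Suppose the narrow PPV is 70%, so the study should stop. The chance of passing is the binomial probability of at least 75% confirmed, when the wider definition adds 0, 5 or 10 percentage points:

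| Points added (assumed) | 80 returns, at least 60 confirmed | 100 returns, at least 75 confirmed |
|---|---|---|
| 0 | 0.20 | 0.16 |
| 5 | 0.56 | 0.55 |
| 10 | 0.89 | 0.91 |

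Five points turn a probable stop into slightly better than an even chance of proceeding.

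**The case against.** **Instability may be corroboration.** The questionnaire goes only to patients who already carry a dislocation code, and the protocol itself sometimes uses traumatic anterior instability as a name for the condition. Accepting the term is partly a design choice, and 'caused by injury' may qualify all three descriptions. This stands as a reason why *u* may be small. It does not make the item able to separate dislocation from lesser instability, which the covering letter says is needed.

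**Appendix H may hold the scoring.** Its figure is not shown, and question 8 presupposes some rule for reading the answers. The link from answers to PPV may therefore exist, and its absence is not claimed here. No rule can split a pooled YES or supply a direction.

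**The net effect is uncertain.** A reader might infer that the questionnaire is bound to overstate the true PPV. The documents do not support that. True dislocations that the notes fail to document pull the other way, and question 8 may catch some of them. The inequality holds only for a narrow definition applied to the same notes.

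**Question 5.** A reader might infer from its identical routing that patients with an earlier dislocation count as confirmed. Routing is not scoring. The answer is recorded, it can be used to exclude such patients, and recurrence data are wanted either way.

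**Appendix D.** The largest code is labelled "Dislocation or subluxation of shoulder", and a reader might take its event count as a measure of misclassification. The counts cover all events recorded in CPRD, not first-time patients aged 16-35, and a combined label does not say how many events were subluxation only.

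**Further safeguards.** Progression also passes through a report to the funder and an external comparison of age-gender rates. Neither can recover the distinction for the sampled patients.

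**Conclusion.** The point holds for three things: the pooling at questions 1 and 4, the missing direction item, and the free-text wording left in Section F. As printed, the questionnaire yields a PPV for a broader condition than the one the 75% rule names.

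The part that can be sized from the protocol is modest: about 4 percentage points at the threshold (75% against 71%), if the 95% anterior figure applies to the confirmed cases. A measured 80% would still pass on direction alone (0.80 × 0.95 = 76%). The instability part could be larger, but the protocol gives no figure for it. The values of 68%, 64% and 57% only illustrate assumed shares of 5%, 10% and 20%. The change should be made before mailing, because answers not collected cannot be reconstructed.

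**What to change.** Before the questionnaires go out:

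1. Split question 1, and likewise question 4, into 'dislocation documented' and 'instability or subluxation only'.
2. Add one item: 'direction: anterior / posterior / not recorded'.
3. In Section F, replace the free-text definition with one based on answers: confirmed means traumatic dislocation documented, not posterior, and question 5 answered NO, as a share of returned questionnaires.
4. Report two secondary figures: the PPV on the broader definition, and the share with direction not recorded. The second matters because 'not posterior' counts unrecorded direction as confirmed.

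The cost is a few tick boxes and one sentence in Section F. The downsides are that the measured PPV may be lower, making a stop more likely, and that some replies will lack direction.

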Main study (WP2): The main study (WP2) will be a population based propensity score-matched cohort study using CPRD and HES collected datasets. The cohort of participants in this study will be young adults (aged 16–35 years) with traumatic anterior shoulder dislocation (T ASD) with at least 2 years data entry in CPRD before the their first shoulder dislocation code and at 2 years follow up from their first dislocation code entry in CPRD. All events and outcomes will be collected using a pre-agreed validated list of READ CODES (CPRD) and OPCS 4.7 CODES (HES). These codes are listed in the appendices and have already been identified. They will be further validated and informed by WP1. The first read code entry in CPRD for shoulder dislocation will be defined as the ‘first dislocation’. These codes will then be routinely linked to patients and to HES.

The ***Intervention group*** will be patients in CPRD with first time T ASD who underwent shoulder stabilisation surgery after their first dislocation (early surgical repair in this NHS context will mean ‘a decision to treat surgically after the first T ASD’ and receiving surgery within 6 months). This means linking HES data to CPRD data in such a way that a HES surgical OPCS 4.7 code is seen to occur after a single first dislocation code in CPRD (without further dislocation codes) before that surgical date. The timelines between first dislocation codes and OPCS 4.7 codes will be recorded. The ***Control group***. While the most desirable control group would be physiotherapy, it is possible that WP1 will reveal that free text notes and referral codes on physiotherapy will be lacking and not reliable. If this is the case then conservative care will be defined as ‘non surgical intervention’ with no linked OPCS 4.7 surgical shoulder codes producing a control cohort of patients whose first time shoulder dislocation has been treated non-operatively. If however free text entries and referral codes for physiotherapy are reliably present in CPRD then conservative care will be physiotherapy identified by physiotherapy referral codes after a first time T ASD code. Any subsequent dislocation codes or OPCS 4.7 surgery code will be recorded.

This project was funded by the National Institute for Health Research Health Technology Assessment (project number 14/160/01).

The views and opinions expressed therein are those of the authors and do not necessarily reflect those of the HTA, NIHR, NHS or the Department of Health.

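### The GP questionnaire skips its recurrence and physiotherapy items when the dislocation is unconfirmed, so it cannot give GP-verified recurrence-code accuracy for the code-defined WP2 cohort

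*Protocol*

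**What the plan says.** **The form (Appendix I).** Q1 asks "Is shoulder dislocation, an unstable shoulder, or shoulder instability caused by INJURY documented in the patient’s notes". A YES there goes to Q5. A NO goes through Q2, where both answers lead on to Q3 (imaging reports) and then, if that is also NO, to Q4: "Do Hospital letters from specialists or physiotherapists confirm traumatic instability or traumatic shoulder dislocation". YES at Q3 or Q4 goes to Q5. NO at Q4 goes to Q8.

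Q5 asks about dislocation before registration at the practice. Q6 asks "Are there any further dislocation codes in the record during the 2 years after the first dislocation code", with Q6b (is each later code a true new episode?) and Q6c (were there uncoded recurrences?). Q7 asks "Are there any physiotherapy treatment codes for 2 years after the first dislocation code", with Q7b and Q7c on whether codes and actual physiotherapy agree. Q8 covers patients who failed the earlier questions: if "your reading of the notes or your knowledge of the patient suggest they might have please tick the YES box". Either answer at Q8 ends the form.

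**The main study.** Section F (Main study) states: "The first read code entry in CPRD for shoulder dislocation will be defined as" the first dislocation. Of the code lists it says "They will be further validated and informed by WP1". The cover letter in Appendix I says of outcome ascertainment: "We will be completely reliant in the main phase of this study on electronic codes to identify recurrences".

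**The progression rule (Section F).** WP2 goes ahead if the PPV of the CPRD codes is at least 75%. Poor coding of first or recurrent dislocations is a reason to stop, but no number is attached to recurrence coding.

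**The concern.** The cover letter gives the form two jobs: to establish whether a coded dislocation was a real traumatic dislocation, and to establish whether later codes are new episodes or reviews of the old problem. The first job is done on every returned form. The second is done only on patients who pass the first.

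WP2 has no equivalent filter. A coded patient whose notes would have failed Q1, Q3 and Q4 still enters WP2 if the other criteria are met, and a later dislocation code in that patient counts as a primary outcome event. These are the patients in whom a later code is least likely to be a true re-dislocation, and WP1 collects no GP judgement about them. The same gap applies to physiotherapy codes, whose reliability decides the definition of the control group (Sections F and J).

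Patients flagged YES at Q8 are a separate loss. The GP thinks they may be genuine cases, yet the form ends without asking about recurrence.

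**Working it through.** **1. Routing.** Following every combination of YES and NO through the printed instructions, Q6 and Q7 are reached if and only if Q1, Q3 or Q4 is YES. No path leads from Q8 back to Q5, Q6 or Q7.

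**2. How many patients.** The protocol gives no accuracy figure for recurrence coding, so there is none to reproduce. Its own limits are:
- 100 patients sampled (Section F), taken here as 100 questionnaires sent;
- an 80% return rate (Protocol Amendment), so 100 × 0.80 = 80 forms;
- PPV of at least 75%, so at most 1 − 0.75 = 25% unconfirmed.

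At that limit 80 × 0.75 = 60 forms have Q5 to Q7c answered and 80 × 0.25 = 20 do not. At 95% confirmed, only 4 of 80 would be skipped.

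**3. Effect on the PPV of recurrence codes.** Let
- c = share of coded patients confirmed;
- a = share of later dislocation codes that are true in confirmed patients;
- b = the same share in unconfirmed patients;
- r = frequency of later codes in unconfirmed relative to confirmed patients.

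Then PPV(all) = [c·a + (1 − c)·r·b] / [c + (1 − c)·r].

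The form estimates a. The gap is a − PPV(all) = (1 − c)·r·(a − b) / [c + (1 − c)·r]. It is positive only if r > 0 and b < a.

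Only the limit c = 0.75 comes from the protocol. The values of a, b and r are assumptions. With a = 0.85:

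| c | r | b | PPV(all) | Gap (points) |
|---|---|---|---|---|
| 0.75 | 0 | any | 0.85 | 0 |
| 0.75 | 1 | 0.85 | 0.85 | 0 |
| 0.75 | 0.5 | 0 | 0.6375/0.875 = 0.729 | 12 |
| 0.75 | 1 | 0 | 0.6375/1 = 0.638 | 21 |
| 0.75 | 1.5 | 0 | 0.6375/1.125 = 0.567 | 28 |
| 0.90 | 1 | 0 | 0.765/1 = 0.765 | 8.5 |

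**4. Other measures.** Sensitivity (Q6c) is not inflated by leaving out patients who had no dislocation to miss. Overall agreement can move either way. If 80% of confirmed patients are correctly classified and a share f of unconfirmed patients carry a (false) later code, agreement over all patients is 0.75 × 0.80 + 0.25 × (1 − f). That is 85% at f = 0, 80% at f = 0.20 and 72.5% at f = 0.50. For physiotherapy codes the documents give no basis for a direction: an unconfirmed patient may well have had coded physiotherapy for the shoulder.

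**The case against.** **The skip has a logic.** Q6b asks whether a later code is a new episode or a review, which presupposes a real index event. Validating the index event first and later codes second is a legitimate design, and accuracy among confirmed cases is a valid quantity if labelled as such. This stands. It does not supply the accuracy that applies to a cohort defined by code.

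**Much of the missing information is in CPRD.** Whether an unconfirmed patient has later dislocation or physiotherapy codes should be visible without asking the GP. Treating all such dislocation codes as false, then as all true, would bound the PPV. This also stands, but the bounds are wide: with c = 0.75, a = 0.85 and r = 1 they run from 0.6375 to 0.6375 + 0.25 = 0.8875. What is lost is the GP's adjudication at Q6b, Q6c, Q7b and Q7c.

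**Few patients may be affected.** The 25% is a stopping limit, not an expectation. Q1 is broad and accepts an unstable shoulder caused by injury. This is fair, and the gap shrinks in proportion.

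**Stronger readings that the protocol does not support.**
- A reader might infer that the outcome accuracy reported to the funder will be too high. The protocol states no such figure and does not fix the denominator of the report.
- A reader might infer that the progression decision rests on a biased number. The only number in the rule is the PPV of the index code, which Q1 to Q4 address on every returned form before any skip.
- A reader might infer that WP2 analyses every coded patient. It applies age, two-year history, two-year follow-up, linkage and surgical criteria, and WP1 may refine the code list.

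**Conclusion.** The point holds as a gap in the information WP1 collects. The form cannot give GP-verified accuracy of recurrence codes, or of physiotherapy codes, for the population WP2 will analyse.

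For recurrence codes, the PPV among confirmed cases probably overstates the PPV in the WP2 population. The expectation rests on reasoning, not data: where the index event was not a traumatic dislocation, later dislocation codes are less likely to be true. The size is unknown. It is zero if unconfirmed patients have no later codes or equally valid ones. It is about 12 to 21 points in the adverse case of 25% unconfirmed, an assumed 85% in confirmed cases, all later codes in unconfirmed patients false, and those codes half as frequent to equally frequent. It would be larger if they were more frequent.

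Inflation is not shown for sensitivity, overall agreement or physiotherapy codes. The 75% index-code criterion is untouched. This is a modest defect, but once the forms have been returned the missing answers can be had only by contacting practices again.

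**What to change.** In Appendix I, change the Q4 instruction so that NO goes to Q5. The existing routing then carries the GP through Q6 to Q7c and on to Q8, so no other instruction needs to change and patients flagged YES at Q8 are covered as well.

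In the WP1 report, give recurrence-code and physiotherapy-code accuracy twice, each with its denominator: over all returned questionnaires, as the figure relevant to WP2, and among confirmed cases.

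The cost is one altered instruction before dispatch and a few extra tick-box items for the minority of GPs whose patient is unconfirmed: at most about 20 of 80 returned forms if the 75% criterion is met. In those patients Q6b may be awkward to answer, because it presumes an earlier dislocation. A short note saying that a later code not reflecting a true dislocation should be answered NO would deal with that.

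### The GP questionnaire never asks about uncoded dislocations between practice registration and the index code, so WP1 confirms first-time status only in part

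*Protocol*

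**What the plan says.** Section F of the Protocol (CPRD Internal Validation) defines first-time patients as "those patients with at least two years of data (washout period) before a first time entry read code for shoulder dislocation". The paragraph on the main study (WP2) carries this forward: "The first read code entry in CPRD for shoulder dislocation will be defined as the ‘first dislocation".

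The internal validation has named tasks, which include "confirming first time shoulder dislocation; confirming traumatic cause; and assessing the subsequent codes used for further events". The stop-go paragraph of the same section says that "if the analysis of the notes indicates that first time dislocation coding and recurrent dislocation coding is poor then the study cannot proceed". It sets the go threshold at a PPV of at least 75%, the percentage being of cases "recorded according to READ/OXMIS codes that are confirmed in the free text search".

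Under Version 2 (Protocol Amendment section) the Appendix I questionnaire replaces the review of 100 sets of notes, with a quoted return rate of 80%. Its Q5 reads: "Is there any record of a dislocation prior to the CPRD first registration date at your practice". Q6, Q6b and Q6c concern the two years after the first dislocation code, and Q6c asks specifically about dislocations in that period that were not coded.

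**The concern.** The questionnaire is now the instrument that has to establish first-time status, yet its one question on earlier dislocations ends at the wrong date for that purpose. Whether the index code was a first dislocation depends on everything before the index code, not only on what came before the patient joined the practice.

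First-time status defines the population for both aims, and surgery after more than one dislocation is an exclusion (section I). Appendix E lists the number of dislocations before surgical repair among the risk factors for re-dislocation after surgery. Patients wrongly taken as first-time would therefore enter WP2 with a characteristic that the plan itself regards as prognostic. WP1 is where the plan intends to detect this and where the result can still stop the study.

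**Working it through.** **Step 1. Compare the time windows.** The plan has no figure to reproduce here; the check is which question covers which period.

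| Period | Coded dislocations | Uncoded dislocations (notes, letters, free text) |
|---|---|---|
| Before practice registration | Q5 | Q5 |
| Registration to index code (at least 2 years, includes the washout) | Ruled out by selection: the index is the first code | No question |
| Index code to 2 years after | Q6, Q6b | Q6c |

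The remaining items do not fill the empty cell. Q1 to Q4 ask whether a traumatic dislocation, instability or injury is documented and are not dated relative to the index code. Q7 concerns physiotherapy and Q8 concerns traumatic status. The three aims in the covering letter of Appendix I do not mention first-time status either.

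That the washout lies after registration is an inference: section F requires at least two years of CPRD data before the first code.

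**Step 2. Can the absence of codes fill the gap?** No. The validation tests codes against what the notes hold. Taking the lack of an earlier code as proof that there was no earlier dislocation assumes what is to be tested. Q6c shows that the authors regard uncoded dislocations as possible after the index code; nothing makes them less possible before it.

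**Step 3. Illustrate the effect on the go rule.** Let u be the share of confirmed cases that had an uncoded dislocation between registration and index code. The documents give no value for u, so a range of 0 to 20% is assumed. Then

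first-time PPV = measured PPV × (1 − u),

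and this equals 75% when u = 1 − 0.75 / measured PPV.

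| Measured PPV | u = 0 | u = 5% | u = 10% | u = 15% | u = 20% | u at which 75% is reached |
|---|---|---|---|---|---|---|
| 80% | 80% | 76% | 72% | 68% | 64% | 1 − 0.75/0.80 = 6.25% |
| 85% | 85% | 80.75% | 76.5% | 72.25% | 68% | 1 − 0.75/0.85 = 11.8% |
| 90% | 90% | 85.5% | 81% | 76.5% | 72% | 1 − 0.75/0.90 = 16.7% |

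**Step 4. The same in patients.** Assume 100 questionnaires, matching the 100 sets of notes they replace, and the quoted 80% return: 100 × 0.80 = 80 forms. The threshold then needs 0.75 × 80 = 60 confirmed.

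- Measured PPV 80% (64 confirmed): four hidden cases leave 60/80 = 75%, which still passes; a fifth gives 59/80 = 73.75%, which fails.
- Measured PPV 90% (72 confirmed): twelve leave 60/80 = 75%; a thirteenth gives 59/80 = 73.75%.

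So the decision is sensitive when the measured PPV is near the limit and fairly robust when it is high.

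**The case against.** The strongest reply is that the design is largely complementary. Selection excludes any coded dislocation in the washout, since such a code would itself have become the index, and Q5 looks at the period that selection cannot reach. This stands. A reader might infer that the whole washout goes unchecked, or that WP1 cannot confirm first-time status at all. The documents do not support that: the gap is confined to uncoded events.

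A reader might also infer from the routing that an earlier dislocation reported at Q5 still counts as a confirmed case, because YES and NO both lead to Q6. That does not follow. Q2, Q6b, Q6c, Q7b and Q7c also send both answers to the same place; this is skip logic, not scoring. The validation algorithm in Appendix H, on which the questionnaire is based, is a figure not available here and may say how Q5 is used. Whatever it says, it cannot use an answer to a question that was not put.

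Section F also plans a sensitivity estimate based on alternative diagnosis codes and a comparison of age-gender rates with other settings. Both bear indirectly on missed dislocations, but neither shows whether a given patient's index code was the first event.

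Finally, the documents supply neither a measured PPV nor a value for u, so any single scenario is arbitrary. That is why a range is shown. Patients who answer YES at Q5 are left out of u because they are observed and can be scored.

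**Conclusion.** The concern holds in a limited form. As worded, the questionnaire would not elicit an uncoded dislocation between registration and the index code, so WP1 confirms first-time status only in part. Any resulting error runs one way: the PPV for first-time dislocation would be overstated.

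The size cannot be determined from the documents. With u assumed, the true figure drops below 75% once u exceeds about 6%, 12% or 17% for a measured PPV of 80%, 85% or 90%. This does not show that the go decision would be wrong, only that WP1 could not tell. The conclusion rests on the wording of Appendix I and on reading the two years of prior data as falling after registration. Because the item feeds a stop-go decision and is easy to correct, it should be changed before the questionnaire is sent.

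**What to change.** Reword Q5 along these lines: *Is there any record, coded or uncoded, of a dislocation of this shoulder before [index-code date supplied]? If yes, was it before registration at your practice, after registration, or both?* Continue to Q6 after either answer.

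State in the scoring rule that a YES is not a confirmed first-time case in the PPV for the 75% threshold, and report the share of index codes that fail on this item. The split at registration keeps the information that Q5 now collects and makes u observable.

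The cost is one reworded question, the index date printed on the form and one scoring line. No extra records are needed. The downside is that the PPV may come out slightly less favourable.
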